9.5. Enrollment/Baseline

When a patient and the PI or authorized designee (if applicable) signs and dates the IC Form, the patient is considered a subject enrolled in the study. The date the subject signed the IC Form (and data protection authorization where applicable) must be documented in the subject's medical records. Enrollment will occur \leq 30 days of post-acute MI. Medtronic should be notified (via Enrollment eCRF) as soon as possible to aid in enrollment tracking. Once consent is obtained, report cardiac adverse events, study deviations, system modifications, and subject deaths as they occur.

The following information is required to be collected at Baseline:

- Patient Informed Consent Date (Enrollment Date)
- Eligibility Verification (Inclusion/Exclusion Assessment)
- Subject Demographics
- Acute MI information
- Medical History
- Cardiovascular Medication categories including Angiotensin-converting enzyme (ACE) Inhibitors, angiotensin receptor blocker (ARB), Beta blockers, Vasodilators, Diuretics, Aldosterone receptor antagonists, Digoxin, Anticoagulation agents, anti-platelet agents, statin, anti-arrhythmics, or any cardiovascular medication categories that will become available during the course of the study.
- LVEF measurement (\leq 14 days post -acute MI) and ECG done as per standard practice. For LVEF, it is recommended to measure by echocardiography (for example Simpson's method) and to use the same method when assessing the same subject at Baseline and 3-month follow-up visit.

9.6. Follow-Up Visits

Table 3 below specifies permitted time windows for the required subject visits. Subject visit target dates and windows for each follow-up will be made available to the study site. Follow-up visit windows are based on days post-acute MI, and the follow-up visit can be performed either in person or via phone. If a subject visit fall outside the pre-specified window, a study deviation must be reported and the original follow-up schedule maintained for subsequent visits.

Data analyses will include follow-up visits, regardless of whether the visits occur within the time window. Therefore, a late visit is preferred over a missed visit but must be accompanied by a deviation.

Table 3: Follow-up windows

Study Follow-up Visit	Window (Calculated days post-acute MI)		
	Window Start (days post-MI)	Target (days post-MI)	Window End (days post-MI)
3 month	40	90	120
6 month	150	180	210
12 month	335	365	395

Complete a Subject Visit CRF for each follow-up visit.

At 3-month follow-up visit, LVEF will be assessed as per standard practice:

- As per Investigator's discretion, if the subjects have LVEF $\leq 40\%$ or meeting one of the referral criteria (sustained VT, cardiac or unexplained syncope, clinically significant palpitations, new onset bundle branch block, conduction abnormalities, or symptomatic bradycardia), the subjects can be referred for SCD risk stratification and management (EP Referred Group). If the referral does not take place, it is not a study deviation.
- If the subjects have LVEF $>40\%$ but $<50\%$ (between 41% - 49%), the subjects will remain in the Non-Referred Group.
- If the subjects have LVEF $\geq 50\%$, they shall be exited from the study.

For the Non-Referred Group, a Referral Status CRF is needed for each subsequent visit unless the subject is referred to the EP Referred Group. During study follow-up visits, the Non-Referred Group subjects can be referred to the EP Referred Group if their LVEF is $\leq 40\%$ or meets one of the referral criteria (as listed above).

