Secondary Objective(s)	
Characterize the proportion of post-acute MI patients who are known to be indicated for an ICD/CRT-D within 12 months post-acute MI.Characterize the proportion of post-acute MI patients who receive an ICD/CRT-D within 12 months post- acute MI.Summarize the referral and implant refusal rationale.Characterize the proportion of post-acute MI patients who experience cardiovascular mortality.Determine how the ejection fraction evolves over 3 months following an acute MI.
Study Design	
This study is a prospective, non-randomized, multi-site, global, post-market study.
 
After enrollment, subjects will be followed up at 3-, 6- and 12-months. The 6- and 12-month follow up maybe completed either in-person or via phone.
 
There is no investigational device; subjects can be implanted, if indicated and referred, with any brand or model of a market released ICD/CRT-D. The study is expected to be conducted at approximately 50 sites worldwide. Participating geographies are: China, India

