9.3. Schedule of Events

Clinical data will be collected at the Baseline 3 month, 6 month, 12 month, and exit visits. In addition if applicable, clinical data will be collected with an exit or death, as well as unscheduled visits. Device data will be collected from device interrogations on Medtronic devices received during the period between the enrollment and exit until study closure; for non-Medtronic devices, device data will not be collected. Data will be collected using eCRFs using an electronic data management system for clinical studies. In addition to eCRF data, non-eCRF data will be collected including device interrogation files (for Medtronic implanted devices only). Surveys may also be used throughout the study.

Data will be stored in a secure, password-protected database, which will be backed up nightly. Data will be reviewed using programmed and manual data checks. Data queries will be made available to study sites for resolution. Study management reports will be generated by Medtronic to monitor data quality and study progress. At the end of the study, the data will be frozen and retained indefinitely by Medtronic. Data Collection requirements are summarized in the table 2 below.

Table 2 Data Collection and study procedure requirements at subject visit

Study Procedure	Baseline	3 month visit	6 month visit	12 month visit	Study Exit
Patient informed consent	X				
Eligibility Verification (Inclusion/ exclusion assessment)	X				
Subject Demographics	X				
Acute MI information	X				
Medical History	X				
Cardiovascular Medications	X	X			
LVEF measurement	X	X*	X (collect if performed as per SOC)	X (collect if performed as per SOC)	
ECG	X	X (collect if performed as per SOC)	X (collect if performed as per SOC)	X (collect if performed as per SOC)	
Referral Status		X	X	X	X
Implant Status (if applicable)		X (if subject receives or has received device implant)	X (if subject receives or has received device implant)	X (if subject receives or has received device implant)	X (if subject receives or has received device implant)
Device Interrogation File (pdd) or CareLink Transmission for subjects implanted with Medtronic device only		X	X	X	X
Adverse Event	As they occur				
System Modification					
Study Deviation					
Subject Death					

* The LVEF measurement needs to be performed ≥ 40 days post-acute MI for MI subjects without revascularization, or ≥ 90 days post-revascularization for post-MI subjects with revascularization done.

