9.6.1. Information Collected

The following information is required to be collected at follow-up visits:

- Referral status
- Implant status
- Cardiovascular Medication categories as listed under Enrollment/ Baseline (for 3-month visit only)

- LVEF measurement as per standard practice.
 - For 3-month visit, the LVEF measurement needs to be performed ≥ 40 days post-acute MI for MI subjects without revascularization, or ≥ 90 days post-revascularization for post-MI subjects with revascularization done.
- ECG as per standard practice
- Cardiovascular Adverse events, Study Deviations and System Modification.

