14.2. Data Management

Data will be collected using Oracle Clinical, an electronic data management system for clinical studies. eCRF data will be stored in a secure, password-protected database which will be backed up nightly. Data will be reviewed using programmed and manual data checks. Data queries will be made available to sites for resolution. Study management reports may be generated to monitor data quality and study progress. At the end of the study, the data will be frozen and will be retained indefinitely by Medtronic.

Only authorized persons can complete eCRFs. eCRFs shall be signed by the Principal Investigator. The Principal Investigator can delegate the CRF sign off task to Sub-Investigators only. Delegation of authority will be specified on the appropriate documentation.

All records and other information about subjects participating in this study will be treated as confidential. Data will be transferred and processed by Medtronic or a third party designated by Medtronic in a key coded form, unless it's impossible to make it anonymous, for instance, where the subject's name cannot be removed from the data carrier.

Procedures in the CIP require source documentation. Source documentation will be maintained at the site. Source documents, which may include worksheets, patient medical records, echo data and device interrogation files, must be created and maintained by the investigational site team.

The data reported on the eCRFs shall be derived from source documents and be consistent with these source documents, and any discrepancies shall be explained in writing. The eCRF may be considered the source for the following data collection elements:

- Enrollment Notification
 - Site assigned patient reference
- Baseline
 - Administrative information
- Adverse Event
 - Date study site became aware of event
 - Relatedness of adverse event
- Deviations

- Reason for deviation

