Appendix A: Case report forms

Case report forms will be provided under separate cover upon request.

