7.9.1.3 Analysis Methods

Subjects will be evaluated during their three months visit (chronic phase, $\geq 40-90$ days after MI) for determination of the need for SCD risk stratification and management. As of this visit, subjects will be partitioned into several groups: died of cardiovascular causes prior to reaching the 3 months visit, exited or died of non-cardiovascular or unknown causes prior to reaching 3 months visit, reached the 3 months visit and exited because of $\text{LVEF} \geq 50\%$, reached the 3 months visit and had at least one reason for referral for SCD risk stratification and management, reached the 3 months visit and had no reason for referral for SCD risk stratification and management.

Subjects classified as “died of cardiovascular causes” will be all subjects with subject status “death” within the exit CRF and with primary cause of death “non-sudden cardiac death” or “sudden cardiac death” within the death CRF.

Subjects classified as “exited or died of non-cardiovascular or unknown causes” will be all subjects with subject status “death” within the exit CRF and with primary cause of death “non-cardiovascular death” or “unknown classification” within the death CRF and all subjects with subject status “adverse event, lost to follow-up, physician decision, sponsor request or withdrawal by subject” in the exit CRF.

Subjects classified as “reached the 3 months visit and exited because of $\text{LVEF} > 50\%$ ” will be all subjects that will have completed the three months visit and will have subject status “other” within the exit CRF and will have a result of LVEF measurement higher or equal than 50% within the LVEF CRF.

Subjects classified as “reached the 3 months visit and had at least one reason for referral” will be all subjects that will have completed the three months visit and that in the referral CRF will have answer “yes” to the question “does the subject meet referral criteria” and will have at least one reason for referral selected underneath the question “if yes, indicate referral criteria met”.

Subjects classified as “reached the 3 months visit and had no reason for referral” will be all subjects that will have completed the three months visit and that will have answer “no” to the question “does the subject meet referral criteria” in the referral CRF.

Descriptive statistics will be used to summarize these groups and displayed as shown in the example Table 2 below.

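### Protocol 9.6 lets the 3-month visit be done by phone, and the SAP has no separate group for a completed 3-month visit without an LVEF

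*Protocol*

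**What the plan says.** **Visit mode.** In the Synopsis (Study Design), "The 6- and 12-month follow up maybe completed either in-person or via phone". Protocol 9.6 states that "the follow-up visit can be performed either in person or via phone", just above Table 3, whose first row is the 3-month visit.

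**LVEF at 3 months.** Protocol 9.6: "At 3-month follow-up visit, LVEF will be assessed as per standard practice". Protocol 9.6.1: "For 3-month visit, the LVEF measurement needs to be performed" at least 40 days after the MI without revascularisation, or at least 90 days after revascularisation. The footnote to Protocol Table 2 sets the same timing. At 6 and 12 months, Protocol Table 2 asks only that an LVEF be collected if it was done as standard of care.

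**Use of that LVEF.** Under Protocol 9.6, a value of 40% or less permits referral, 41-49% keeps the subject in the Non-Referred Group, and 50% or more ends participation.

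**Classification.** SAP 7.9.1.3 defines five groups. The no-reason group takes every subject who has "completed the three months visit and that will have answer “no” to the question “does the subject meet referral criteria” in the referral CRF". No LVEF value is required. SAP 7.4 says that the main analyses do not account for missing data.

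**The concern.** A site that follows Protocol 9.6 literally can complete the 3-month visit by phone without a visit-mode deviation, yet the measurement on which the visit turns cannot be made by phone. The Synopsis suggests that the phone option was meant for the later visits only, and sites are left to resolve the difference themselves.

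The consequence appears in SAP Table 2, which belongs to the primary objective. A subject with no 3-month LVEF might have had a value of 40% or less (a reason for referral), 41-49% (none) or 50% or more (exit). A no on the referral CRF places that subject in the no-reason row, so an unknown is reported as a known negative. The same subject is absent from the denominator of the proportion referred, which counts only subjects with a recorded criterion.

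**Working it through.** **1. Where each 3-month completer goes under SAP 7.9.1.3**

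| Referral CRF answer | LVEF at 3 months | SAP group |
|---|---|---|
| Yes, any criterion | Measured, early or absent | Reason for referral |
| No | 41-49% | No reason |
| No | Absent or too early | No reason |
| Blank | Absent | None |

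Subjects who exit with 50% or more have their own group. The second and third rows of this table are merged in SAP Table 2.

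**2. A second route to the same result.** The 3-month window in Protocol Table 3 runs from day 40 to day 120, which is 120 - 40 + 1 = 81 days. For a subject revascularised on the day of the MI (an assumption), an LVEF on days 40 to 89, which is 50 days, is too early under Protocol 9.6.1. An in-person visit can therefore also end without a qualifying LVEF. This is a count of days, not a frequency; the target is day 90.

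**3. The plan's sample size reproduced.** Inputs from SAP 6.1: 95% Wilson interval, half-width 0.125, proportion referred 0.70, 30% with a reason, 10% lost by 3 months.

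Half-width for x of n, with p = x/n and z = 1.96: z × sqrt(p(1-p)/n + z²/(4n²)) / (1 + z²/n). Summing the Binomial(n, 0.70) probabilities of all x with half-width at most 0.125 gives 0.784 at n = 53 and 0.897 at n = 54. So 54 is the first n to reach 0.80. Then 54/0.30 = 180 visits and 180/0.90 = 200 enrolled. The plan's figures reproduce.

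**4. Illustration.** The documents give no frequency. Assume 10 of the 180 visits lack a qualifying LVEF, all are answered no, the planned 30% of these subjects have a reason, and none of those reasons is detected.

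- Hidden reasons: 10 × 0.30 = 3, leaving 54 - 3 = 51 recorded.
- Recorded share with a reason: 51/180 = 0.2833, against 0.300.
- With 51 fixed, the probability of meeting the half-width is 0.65. The half-width at an observed 70% moves from 0.119 (n = 54) to 0.122 (n = 51).
- For scale, the count with a reason varies by chance anyway: sqrt(180 × 0.30 × 0.70) = 6.1.

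**5. Does SAP 6.2 need to change?** Its formula is N = 54 / share with a reason / (1 - exit rate), where the share is taken over all completed 3-month visits.

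- As written: 54/0.2833 = 190.6 visits, and 190.6/0.90 = 211.8, so about 212 enrolled. Expected recorded reasons: 190.6 × 0.2833 = 54.
- With the unmeasured visits left out: 51/170 = 0.300, which returns 200 enrolled and leaves the region at 51, where the probability is 0.65 against the 80% target.

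The existing denominator compensates; excluding these visits would remove that.

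**The case against.** The strongest reply is that phone contact is not the cause. The 3-month LVEF is required whatever the visit mode, and an echocardiogram can be done on another day. A missed or mistimed one departs from the protocol, must be reported with an explanation under Protocol 9.10, and is tabulated by category under SAP 7.1.2. Protocol 14.2 adds that "Data will be reviewed using programmed and manual data checks". SAP Table 9 counts subjects with a measurement, and SAP section 9 promises counts of missing data. The study is descriptive, with no hypotheses.

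All of this stands, and it keeps the point small. What it does not do is change the row: no stated control moves an unmeasured subject out of the no-reason group. Whether a no without an LVEF would be blocked or queried cannot be seen, since "Case report forms will be provided under separate cover upon request".

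A reader might infer three stronger things, none of which the documents support:

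- **That 9.6 waives the LVEF when the visit is by phone.** It does not; 9.6, 9.6.1 and Protocol Table 2 all keep the requirement.
- **That the SAP leaves these subjects unclassified.** Only a blank CRF answer does so. A no goes to the no-reason group, and a yes on a symptom, ECG or early-LVEF criterion goes to the reason group. The gap is the lack of a separate group.
- **That SAP 6.2 should exclude unmeasured visits.** Step 5 of the working shows that this would stop the formula from making up the shortfall.

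**Conclusion.** The point holds as a minor one. Protocol 9.6 and the Synopsis differ on whether the 3-month visit may be by phone, and SAP Table 2 pools subjects whose LVEF is unknown with subjects measured at 41-49%.

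The documents give neither the number of such visits nor the direction of any effect on the proportion referred. The loss of 3 of 54 subjects rests on an assumed 10 visits, the planned 30% rate and no detection of any reason. The last is pessimistic, because a phone call can elicit syncope or palpitations. The 0.65 also treats the count as fixed and assumes no re-assessment. Re-assessment under SAP 6.2 is optional; if done, the cost becomes about 12 more subjects in that region (212 - 200). The plan's figures of 54, 180 and 200 are not in question.

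**What to change.** 1. **Protocol 9.6.** Limit the phone option to the 6- and 12-month visits, as in the Synopsis, or allow it at 3 months only when an LVEF meeting the timing in the Protocol Table 2 footnote is on file.
2. **SAP 7.9.1.3 and SAP Table 2.** Split the no-reason group so that subjects with a CRF no and no LVEF at the required timing have their own row. Any subject whose CRF records a criterion as met, including on an early LVEF, stays in the reason group. This step also covers the in-person route, which step 1 does not.
3. **SAP 6.2.** Keep the formula and its denominator of all completed 3-month visits.

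The cost is one sentence in the protocol, plus one group definition and one table row in the SAP. Because Protocol 14.6 requires approvals for any revision, the sentence could go in with the next amendment. The downside is some visit-mode deviations or missed visits among subjects reachable only by phone at 3 months; the on-file option limits this.

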9.6.1. Information Collected

The following information is required to be collected at follow-up visits:

- Referral status
- Implant status
- Cardiovascular Medication categories as listed under Enrollment/ Baseline (for 3-month visit only)

- LVEF measurement as per standard practice.
 - For 3-month visit, the LVEF measurement needs to be performed ≥ 40 days post-acute MI for MI subjects without revascularization, or ≥ 90 days post-revascularization for post-MI subjects with revascularization done.
- ECG as per standard practice
- Cardiovascular Adverse events, Study Deviations and System Modification.

9.6.2. Subjects with Medtronic device

Subjects who are indicated for a device and ultimately receive an implant will not be required to be implanted with a Medtronic device. However, if the subject is implanted with a Medtronic ICD or CRT-D, a device interrogation (save-to-disk) will be performed at implant and study follow-up visits, or via CareLink transmission as applicable.

It is recommended that data are not cleared during any interrogation or save-to-disk. Retain one copy at site for the subject file and submit the other copy to Medtronic via Medtronic Secure Messaging (MSM).

9.7. Study Exit

At 3-month follow-up, if a subject has an LVEF $\geq 50\%$, the subject will be exited from the study. Subject who remain in the study after 3-month follow-up should remain in the study until the 12-month follow-up is completed or until all data required to meet study objectives have been collected (whichever comes first). Either an in-office visit or phone call is required for study exit.

A study exit eCRF is required for all subjects. Prior to exiting a subject from the study, it is recommended to follow the subject until all AEs are resolved. Following exit, subjects will continue to receive standard medical care. Upon exiting from the study, no further study data will be collected or study visits will occur for the subject. Exited subjects will not be replaced with newly enrolled subjects.

Subjects are urged to remain in the study as long as possible, but may be exited from the study for any of the following situations:

- Study closure
- Subject lost to follow-up (refer to Section 9.11.1)
- Subject did not meet inclusion/exclusion criteria
- Subject did not provide consent or data use protection authorization
- Subject chooses to withdraw (refer to section 9.11.2 for more information)
- Investigator deems withdrawal necessary (e.g. medically justified, inclusion/exclusion criteria not met)
- Subject exited study at the 3 months visit if the 3-month LVEF is $\geq 50\%$
- Subject completed study after 12 months visit
- Subject Death

For study exit visits the following information is required:

- Reason for exit
- Final interrogation file (or CareLink transmission) for subjects implanted with Medtronic device
- Cardiovascular Adverse events, Study Deviations and System Modification

9.8. Assessment of Safety

This study is related to guideline-based care, using only market approved therapies, and so there are no pre-specified objectives relating to patient safety. Deaths and cardiovascular related adverse events, will be collected. See section 11 for further details.

9.9. Recording Data

The study will collect data using Oracle Clinical, an electronic data management system for clinical studies. Sites will enter data onto electronic case report forms (eCRFs), and the principal investigator or his/her authorized designee(s) will sign off the data entered.

Device interrogation files collected via electronic media at office visits will be sent to Medtronic. Device data from CareLink transmissions will be uploaded to secure servers. Upon receipt via transmissions or electronic media, device data will be maintained with databases and retrieved for analysis and reporting.

Data reported on the CRFs shall be derived from source documents, which may include worksheets, patient medical records and device interrogation/save-to-media files. These source documents must be created and maintained by the investigational site team. Further detail on data management is provided in Section 14.2.

